#### **Unblinding Procedures:**

Emergency Unblinding is appropriate in the unlikely situation of a medical emergency (as determined by the PI or treating physicians, APPs) where knowledge of the treatment allocation is likely to have a significant effect on the clinical management of the enrolled subject and would be instrumental in immediate treatment decisions. In an emergency, it may not be feasible to obtain prior approval from the PI. In this case, after the subject is successfully unblinded, there must be clear documentation explaining why unblinding was necessary. The PI, IRB, and Research Practice Manager will be notified as soon as possible.

Accidental Unblinding: If a subject is accidentally unblinded, clear documentation of events must be recorded, as well as communication with the PI and Research Practice Manager. The treatment assignment must not be revealed to any other members of the study staff, pharmacy staff, or to the subject, unless written approval from the study sponsor is obtained. Every effort should be made to maintain what remains of the blind. In this case, a protocol deviation should be reported to the IRB of record.

Interim Analysis: Patients will be unblinded for the interim analysis by a member of the Department of Biostatistics. The interim analysis will determine if a dose escalation is indicated. Once the partial analysis is complete, the study we resume either at the same dose of

methadone (0.1mg/kg age ideal body weight or an increased dose 0.15mg/kg age ideal body weight).

Primary and secondary endpoint data collection will occur while the study team is blinded with exception of the interim analysis. Once all patients have completed the all parts of the study, final unblinding will occur.

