- 2. Analyze post-operative outcomes including post-operative opioid utilization and pain scores in the first 7 days after surgery. Our working hypothesis is that those patients who receive a single intraoperative methadone dose will have statistically less postoperative opioid utilization and pain scores, without a greater incidence in adverse events (respiratory depression or excessive sedation).

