#### **Design & Procedures**

Study Design: Single center, randomized, double blind, parallel-group dose escalation investigation. All patients will receive standard monitoring for anesthesia and postoperative care. Surgical and anesthesia care (except for intraoperative opioid management) are not altered for study purposes. Subjects are randomized 2:1 to either long-duration (methadone) or short-duration opioid (fentanyl, hydromorphone). The use of any short acting opioid (ie: fentanyl, hydromorphone or both) is considered the control group and total dose, timing of administration, frequency of administration, and dose per administration of either/both short acting opioids will be administered at the discretion of the anesthesiologist as per standard of care practice. Because methadone analgesia for pediatric tonsillectomy has not previously been studied, this pilot study will use escalating dose groups to determine the optimal dose for this procedure. In order to achieve this, our trial design will include two periods. In the first period, we will randomly assign 20 patients to methadone 0.1 mg/kg and 10 patients to typical shortduration opioid (controls). An interim analysis will be conducted to determine if we should escalate to the higher dose of methadone. Methadone dose escalation to 0.15mg/kg age ideal body weight will occur if there is no difference in non-methadone PACU opioid use and no increased adverse events. If proceeding to the second period, we will recruit 20 patients for 0.15 mg/kg methadone and 10 patients as controls. Sample size for this pilot investigation was based on prior studies.

Defining an optimal dose of methadone is a crucial aim of this study, which will allow for future investigations, but is not a primary or secondary outcome. The dose finding nature of this study requires interim assessments after each methadone dose cohort. After the first 20 methadone subjects at 0.1mg/kg age ideal body weight, there will be a planned partial analysis of PACU opioid use. Methadone dose escalation to 0.15mg/kg age ideal body weight will occur if there is no difference in non-methadone PACU opioid use and no increased adverse events. Sample size for this pilot investigation was based on prior studies.

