Pre-operative, Intra-operative, Post-operative Care: Anesthesia and surgical care are not altered for this study except for randomization to the study drug. Oral or IV midazolam for anxiolysis may be given at standard dosing. Anesthetic induction via inhaled sevoflurane or intravenous agents are to be given at the anesthesiologist's discretion.

Patients in the short-duration opioid group receive short-duration opioids (IV fentanyl and/or hydromorphone), given as needed throughout the intraoperative period, per usual practice at practitioner's discretion. Patients in the long-duration opioid group receive IV methadone HCl at 0.1mg/kg. These subjects receive methadone as their only intraoperative opioid, given as a single bolus at anesthetic induction. If needed, a second cohort will receive or 0.15mg/kg of age-based ideal body weight. Following extubation, patients may receive incremental doses of

0.1mg/kg up to a maximum of 0.5mg/kg of dexmedetomidine (dosed at age-based ideal body weight) for sedation if needed, contingent upon adequate ventilatory rate.

For analgesia in the Post-Anesthesia Care Unit (PACU), patients in both groups may receive typical short-duration opioids (fentanyl or hydromorphone) as per usual routine care. It is not necessary that patients receive the same opioid postoperatively as intraoperatively. Post-op opioids orders are written by the pediatric anesthesiologist and opioids are given by PACU nurses per standard practice, based on developmentally appropriate pain scales (FLACC, Wong-Baker Faces, VAS) and institutional practice.

Pain scores via developmentally appropriate and validated pediatric pain scales will be confirmed by a blinded research coordinator OR a blinded secondary pediatric PACU nurse and charted in the EMR prior to administration of opioid analgesics. Adverse events will be recorded by a research coordinator who is blinded to randomization allocation and include: Respiratory depression (respiratory rate <10/min), reintubation, decreased oxygen saturation <85% for 30 seconds, excessive sedation (Pasero Opioid-induced Sedation Scale (POSS) score 3>1 hour, 4>15 minutes), unexpected PICU admission, and vomiting in PACU.

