#### Protections against Risk:

- i) Eligibility criteria exclude patients with known renal or hepatic disease, which may affect opioid disposition, pregnant females, those with severe sleep apnea with apnea hypopnea index > 10 and those who require planned ICU admission post operatively.
- ii) Methadone dosing is fixed, using age based ideal body weight, rather than actual body weight, to obviate risk of excessive dosing due to obesity.
- iii) Dose escalation will only occur if there are no adverse events in the initial dosing group

- iv) If nausea and/or vomiting occur, patients will be treated using the standard of care for all post-anesthesia nausea and vomiting. Respiratory depression with a respiratory rate <10 breaths/minute or hypoxia with oxygen saturation less than 85% for > 30 seconds will be monitored closely. If treatment is required, naloxone will be used. Patients will be routinely monitored by pulse oximetry, and receive supplemental oxygen if dictated, according to standard anesthesia practice.
- v) Research subjects will receive pre-operative, intra-operative and post-operative routine monitoring by anesthesiology and nursing staff.
- vi) The risk of breach of protected health information will be minimized by limiting the number of people within the research group who have access to identified data which will be described in the data monitoring safety plan.

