### **Data Analysis & Statistical Considerations**

Descriptive statistics for each treatment group will be computed for patient demographic and characteristic variables. Since our randomization scheme will have balanced the age effect between treatment groups, we anticipate the demographic and patient characteristic variables will be balanced across groups. For the continuous outcome measures (primary and most of secondary outcomes), we will conduct two-sample t-test to test the outcome difference (e.g., total OME difference) between treatment groups. For categorical outcomes (e.g., PACU side effects and adverse events), chi-square or Fisher exact tests will be applied as appropriate. Considering this is a pilot study for dose finding, we will relax the significance threshold to 0.1 for the interim analysis. Using the primary outcome, total OME/kg as an example, a two-sample t-test will be performed for comparing total OME difference between 20 methadone (0.1mg/kg) treated patients to 10 controls based on significance threshold of 0.10. If methadone showed significant effect on the outcome measure, the higher dose arm (0.15 mg/kg age ideal body weight) will be pursued. In the final analysis, similarly, two-sample test

will be used to test the total OME difference between methadone and control groups for both dose levels. To correct for multiple testing, the significance threshold in the final analysis will be set at 0.025. If there are covariates showing significant difference between treatment groups, we will perform multivariable linear regression analysis to test the treatment effect after adjusting for one selected covariate and examine if the treatment effect remains the same as that found in the two-sample t-test. The reason to restrict to one covariate in the model was to avoid model overfitting considering there will be only 20 samples per group. Similar analysis strategy will be applied to other outcome measures.

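### Two conflicting safety conditions govern methadone escalation, and the interim outcomes listed under Unblinding Procedures include no pause for excess serious events at 0.1 mg/kg

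*Combined protocol and SAP*

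**What the plan says.** The safety side of the escalation decision appears in four places.

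- **Design & Procedures, Study Design** (stated twice): escalation to 0.15 mg/kg needs "no difference in non-methadone PACU opioid use and no increased adverse events". No comparator, test or threshold is given; the natural comparator is the concurrent control arm.
- **Protections against Risk, item iii**: "Dose escalation will only occur if there are no adverse events in the initial dosing group". This is an absolute condition on the methadone arm.
- **Data Analysis & Statistical Considerations**: "If methadone showed significant effect on the outcome measure, the higher dose arm (0.15 mg/kg age ideal body weight) will be pursued". No safety condition is attached.
- **Unblinding Procedures, Interim Analysis**: "Once the partial analysis is complete, the study we resume either at the same dose of" 0.1 mg/kg, or at the increased dose of 0.15 mg/kg. No third outcome is listed.

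The adverse event list in Design & Procedures (perioperative care paragraph) runs from respiratory depression, reintubation, desaturation and excessive sedation to "unexpected PICU admission, and vomiting in PACU".

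Two phrases in Design & Procedures leave open that a second cohort may never be enrolled: "If proceeding to the second period" and "If needed, a second cohort will receive or 0.15mg/kg of age-based ideal body weight". Neither is linked to a safety finding.

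**The concern.** The interim is the only planned point during enrolment at which data are unblinded by arm. Anesthesia providers know each child's drug, and naloxone, oximetry and emergency unblinding protect individual children. None of these shows how events are distributed between arms.

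With two conditions on file, whoever runs the interim could justify either decision from the protocol on the same data. If an excess of serious events is seen, the section that describes what happens next offers only more methadone. The document itself says methadone has not been studied in pediatric tonsillectomy, and its IND-exemption argument (Study Interventions) cites the escalation criteria as a safeguard and calls them specific. They should therefore be single and specific.

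**Working it through.** **Plan's own figures.** The plan gives no operating figure for its safety rule. Its only computed figures are the powers for opioid use. They reproduce with a two-sided, equal-variance t-test, noncentrality d / (SD × √(1/n1 + 1/n2)):

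- Interim: 0.3 / (0.3 × √(1/20 + 1/10)) = 2.58, alpha 0.10, power 80.9% (stated 80%).
- Final: 0.31 / (0.3 × √(1/20 + 1/20)) = 3.27, alpha 0.025, power 82.0% (stated 82%).

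They do not bear on the safety decision.

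**Step 1. Do the conditions conflict?** Inputs: 20 methadone and 10 control children at the interim (Design & Procedures). Take 2 methadone children and 1 control child with an event: 2/20 = 10% and 1/10 = 10%. There is no increase, so the comparative condition is met. There are events in the methadone group, so the absolute condition fails. This needs no test and no assumed rate.

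**Step 2. Exposure if the study resumes at the same dose.** Inputs: recruitment goal 60 (Subject Recruitment and Compensation), 30 enrolled by the interim, and 2:1 allocation assumed to continue. (60 − 30) × 2/3 = 20 further children at 0.1 mg/kg, as an upper bound.

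**Step 3. How far apart are the conditions?** The documents give no event rates, so the rates below are assumptions. Three readings are compared:

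- Absolute: barred if any methadone child has an event; probability 1 − (1 − p)^20.
- Numerical: barred if the methadone proportion exceeds the control proportion; sum of Binomial(20, p1) × Binomial(10, p0) over all pairs with a/20 > b/10.
- Fisher: barred only if the increase is significant by two-sided Fisher at 0.10. This is an assumed reading that borrows the test and interim threshold from Data Analysis & Statistical Considerations.

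Probability that escalation is barred:

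| True rate, methadone vs control | Absolute | Numerical | Fisher |
|---|---|---|---|
| 5% vs 5% | 64% | 41% | 0.02% |
| 10% vs 10% | 88% | 44% | 0.4% |
| 20% vs 20% | 99% | 45% | 2.2% |
| 20% vs 5% | 99% | 87% | 12% |

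At 2% in both arms the absolute reading bars 33% and the numerical reading 27%. On the Fisher reading with no control events, 5/20 is not enough (p = 0.140) and 6/20 is the first count that is (p = 0.074). The readings therefore range from a rule often triggered by chance to one that misses most true excesses.

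**The case against.** The strongest reply is that the conflict resolves itself conservatively. Zero methadone events cannot be an increase, so the absolute condition implies the comparative one. Since it is phrased as a necessary condition, applying both gives the stricter rule, and the discrepancy errs toward not escalating. That is a fair reading, but the document does not say that both apply, the statistical section's escalation sentence cites neither, and the stricter rule as written lets one vomiting child block the dose step.

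A reader might also infer that excess serious events at 0.1 mg/kg have no consequence, or that the trial could not stop. The documents do not support that. Barred escalation is itself a consequence. Design & Procedures describes a second period only at 0.15 mg/kg, Study Interventions derives three groups of 20 from two anticipated dose cohorts, and the power calculation is conditional on reaching the higher dose. No section provides for 40 children at 0.1 mg/kg or an analysis of them, so the trial could simply end. Protections against Risk also mentions a data monitoring safety plan. It does so only for access to identified data, but a pause rule there cannot be ruled out.

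What remains is narrower. The wording conflict lies within this document, Unblinding Procedures does list resumption at the same dose, and no section connects a pause or stop to a safety finding. Data & Safety Monitoring covers data storage and routine patient monitoring only.

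**Conclusion.** The point holds as a defect in stated rules and should be corrected before the interim. Two safety conditions give opposite decisions on the same data (2/20 vs 1/10), and this rests on no assumption beyond reading the comparative condition against controls. On the terms of Unblinding Procedures, an excess of serious events at 0.1 mg/kg bars escalation but is followed by more dosing at that dose. The figure of up to 20 further children assumes enrolment continues 2:1 to 60, and would be zero if the trial ended instead. The probabilities in the working are illustrative because no event rates are given. The point does not extend to a claim that the trial lacks any means of stopping.

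**What to change.** **(a) One escalation condition.** State it in Design & Procedures and in Protections against Risk, and cross-reference it in Data Analysis & Statistical Considerations and Unblinding Procedures. Base it on the number of children per arm with a serious respiratory or sedation event from the existing list: respiratory depression, reintubation, desaturation, excessive sedation or unexpected PICU admission. Vomiting alone should not bar escalation. This fits Aim 2, whose safety hypothesis names respiratory depression and excessive sedation. For these events, keep the condition at least as strict as the numerical comparison: no escalation if the methadone proportion exceeds the control proportion or, if the sponsor keeps the absolute rule, if any such event occurs on methadone.

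A fixed count such as at least 3 of 20 and a higher proportion than controls may look like a sensible compromise, but as an escalation bar it would loosen the protocol. It permits 0.15 mg/kg after 2/20 vs 0/10, which both the absolute and the numerical readings forbid. At assumed rates of 10% vs 1% it bars escalation 32% of the time, against 88% and 82%.

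**(b) A separate third interim outcome in Unblinding Procedures.** If serious events on methadone exceed controls by a margin that the clinical team sets before the interim, higher than the escalation bar, methadone dosing pauses for safety review before any further child is dosed. Below that margin, not escalating and continuing at 0.1 mg/kg stays available.

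**Cost.** This is protocol wording, applied at an interim that already unblinds, using data already collected and adding no efficacy test. The downside is a false bar or pause. With equal true rates of 2% to 20%, the numerical bar triggers in 27% to 45% of trials. A false pause must be rarer than that because its margin is higher, but its probability depends on the margin chosen and on unknown event rates. A pause also tells the blinded team that there is a methadone-side signal, though not any child's allocation.

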Power calculation: Two-sample t-test with an assumption of equal variance between groups was used to estimate statistical power. For the interim analysis based on 20 methadone 0.1mg/kg cases and 10 controls, assuming standard deviation (SD) total OME as 0.3, our proposed sample size will have 80% power to detect 0.3 OME difference at the significance level (alpha) of 0.1. Assuming we can move forward to the higher dose cohort, the final analysis will include two tests to compare 20 cases vs. 20 controls for each methadone dose level. In this scenario, assuming the same OME variability of SD=0.3 and the reduced alpha level to 0.025, our proposed sample size (N=20/group) can detect the 0.31 OME difference between methadone and control groups with 82% power, a similar effect size as the interim analysis. The detectable mean difference will increase if the OME variability (SD) increases.

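### The plan does not settle whether enrolment continues if the methadone dose is not raised, and its 0.025 final threshold has no exception for a single-dose analysis

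*Combined protocol and SAP*

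**What the plan says.** **Continuation after the interim.** Design & Procedures gives the interim one purpose: "An interim analysis will be conducted to determine if we should escalate to the higher dose of methadone". It then says: "If proceeding to the second period, we will recruit 20 patients for 0.15 mg/kg methadone and 10 patients as controls". The care paragraph of the same section is also conditional: "If needed, a second cohort will receive" the higher dose. Neither place mentions further enrolment at 0.1 mg/kg, and neither says that enrolment stops. Unblinding Procedures, under Interim Analysis, says "the study we resume either at the same dose of" methadone or at the increased dose. Subject Recruitment and Compensation sets a goal of 60 completing patients with no condition attached, and Purpose of the Study also speaks of 60 children.

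**When the dose is raised.** Design & Procedures says escalation "will occur if there is no difference in non-methadone PACU opioid use and no increased adverse events". Data Analysis & Statistical Considerations says: "If methadone showed significant effect on the outcome measure, the higher dose arm (0.15 mg/kg age ideal body weight) will be pursued".

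**Final analysis.** Data Analysis & Statistical Considerations describes methadone vs control tests at both dose levels, and adds: "To correct for multiple testing, the significance threshold in the final analysis will be set at 0.025". The power paragraph, on the premise that the higher-dose cohort goes ahead, says "the final analysis will include two tests to compare 20 cases vs. 20 controls for each methadone dose level". No section gives the sample size, comparison, threshold or power of a final analysis when the dose has not been raised.

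**The concern.** The plan foresees that the dose may not be raised but does not say what trial follows. A team working from Design & Procedures could close enrolment after the first period. A team working from Unblinding Procedures and the recruitment goal would enrol a second cohort at 0.1 mg/kg.

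The analysis of that branch is also undefined. The only stated final threshold is a correction for two tests, and read literally it would apply to a single test too. Because allocation is unblinded for the interim, whatever is left open could be decided after the first-period result is known. The sample size, the comparison and the threshold should therefore be fixed beforehand.

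**Working it through.** **Inputs.** From the power paragraph: SD 0.3; differences of 0.30 (interim) and 0.31 (final); equal-variance two-sample t-test. From the analysis section: alpha 0.10 at the interim and 0.025 at the end. From Study Interventions: 2:1 allocation in each cohort.

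**Formula.** Two-sided power from the noncentral t distribution with n1 + n2 − 2 degrees of freedom and noncentrality δ / (SD × √(1/n1 + 1/n2)).

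**Reproducing the plan's figures.**
- Interim, 20 vs 10, δ = 0.30, alpha 0.10: noncentrality 0.30 / 0.1162 = 2.58, power 80.9% (plan: 80%).
- Final, 20 vs 20, δ = 0.31, alpha 0.025: noncentrality 0.31 / 0.0949 = 3.27, power 82.0% (plan: 82%).

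Both agree, so the plan's method is the two-sided t-test.

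**The branch without escalation.** Two readings are possible.

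*Enrolment continues.* Assume a second cohort of 20 + 10 at 0.1 mg/kg, pooled with the first. That gives 20 + 20 = 40 methadone and 10 + 10 = 20 controls, total 60. The standard error is 0.3 × √(1/40 + 1/20) = 0.0822.

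*Enrolment ends after the first period.* The comparison is 20 vs 10, total 30, with standard error 0.1162.

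| Comparison | Difference | Power at 0.025 | Power at 0.05 |
|---|---|---|---|
| 40 vs 20 | 0.30 | 90.8% | 94.8% |
| 40 vs 20 | 0.31 | 92.6% | 96.0% |
| 20 vs 10 | 0.31 | 62% | 73% |

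At 40 vs 20 the stricter threshold costs 94.8 − 90.8 = 4.0 points at 0.30, and 96.0 − 92.6 = 3.4 points at 0.31. At 0.025 and a difference of 0.31, the two readings of enrolment differ by about 93 − 62 = 31 points and fall on either side of the planned 82%.

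**Is 0.05 defensible for a single test?** 0.05 / 2 = 0.025, so the stated threshold is a two-test correction. The overall level of 0.05 is inferred from 2 × 0.025; the plan does not state it. The whole two-branch design was simulated with no true effect: 400,000 trials, shared controls, first-period data reused, enrolment resumed in both branches, 0.025 per test if both doses are studied. The adverse-event condition was not modelled. The chance of any false positive was:

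| Escalation rule | Single-dose test at 0.025 | Single-dose test at 0.05 |
|---|---|---|
| Data Analysis: raise if interim significant | 0.033 | 0.048 |
| Design & Procedures: raise if no difference | 0.038 | 0.048 |

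A second simulation gave about 0.047 with 0.05 under either rule. Under the Design & Procedures rule, the single-dose branch can follow a significant interim. Given that route, the conditional false-positive rate is about 15% at 0.025 and 25% at 0.05, because the first-period data are reused.

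**The case against.** The strongest reply is that 0.025 was never meant for a single-dose analysis. It follows directly on tests at both doses, its stated reason is multiple testing, and the power paragraph ties it to the scenario in which escalation occurs. That is fair: the firmer defect is silence about the other scenario. Even so, the threshold sentence refers to the final analysis without exception, so a literal reader would apply 0.025.

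It can also be said that a stricter threshold inflates no error, and that at the planned differences it leaves power above 90% if 60 patients are enrolled. Both statements are correct.

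Three stronger readings are tempting but not supported.

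- **That Design & Procedures stops the trial at 30.** It never says so. The recruitment goal and Purpose of the Study both say 60 without condition, which favours continuation. The conflict is by implication only.
- **That 40 vs 20 is the planned comparison.** It is derived from the 2:1 ratio and a second cohort of the same size, and it assumes pooling.
- **That the branch is reached exactly when the first-period result is equivocal, so that lost power matters most there.** This fits only the rule in Data Analysis. Under Design & Procedures, non-escalation follows a detected difference or increased adverse events. The two rules are opposite, and the documents do not show which governs.

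Finally, the conditional rates of 15% and 25% show that 0.05 is not self-evidently right for this branch. It needs the argument from the overall rate.

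**Conclusion.** The point holds as a gap with an implied contradiction. The plan does not settle enrolment, comparison, threshold or power when the dose is not raised. The larger consequence is the enrolment question: at a difference of 0.31 and alpha 0.025, power is 62% if the trial ends at 20 vs 10 and about 93% at 40 vs 20. The threshold matters less. It is conservative for a single test and costs 3 to 4 points at the planned differences.

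These figures rest on SD 0.3, no dropout, an overall two-sided level of 0.05 inferred from the plan, and, for 40 vs 20, a pooled second cohort of 20 + 10.

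**What to change.** 1. Reconcile Design & Procedures, Subject Recruitment and Compensation, and Unblinding Procedures on what follows when the dose is not raised, including when adverse events are the reason. State the resulting sample size.
2. Reconcile the opposite escalation rules in Design & Procedures and Data Analysis & Statistical Considerations, since they decide when this branch is reached. Which rule applies is for the sponsor to settle.
3. In Data Analysis & Statistical Considerations, state that 0.025 applies only if both doses are studied, and that otherwise the final analysis is one methadone vs control test at two-sided 0.05 on all patients. State the intended overall level, and justify the choice by the overall false-positive rate (about 0.047 to 0.048 under either rule if enrolment resumes). Note the higher rate conditional on a significant interim.
4. Add this branch's sample size and power to the power paragraph.

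The cost is protocol and SAP wording. The statistical changes add no patients or procedures.
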